7.4.6.9 Exploratory EFS Analysis

Based on the proposed revised IWG response criteria (Zeidan 2023, Appendix 2), EFS is defined as the time from the date of study randomization to the date of the first of the following events:

- PD (based on the criteria in IWG 2023)

- Failure to achieve CR, PR, CR_L, CR_h, or HI within 6 months of study entry
- Relapse from CR, PR, CR_L, CR_h, or HI
- Death from any cause

EFS (months) = (date of event - date of study randomization + 1) / 30.4375.

EFS analysis will be performed as specified in Section 7.4.5.7 for the ITT Analysis Set.

7.4.6.10 Exploratory Comparison of Response Categories and TI

The TI status (achieved TI versus did not achieve TI) of participants in the mITT Analysis Set will be summarized by treatment group for the following response categories: best overall response of CR by Cycle 7 Day 1, CR or PR, mCR with HI, mCR without HI, HI (in participants not achieving CR, PR, or mCR), and participants without a response.

7.4.7 Statistical/Analytical Issues

7.4.7.1 Interim Analysis

There will be 2 planned interim futility analyses, 1 for the CR and 1 for OS, respectively; these will be non-binding and will be conducted by the IDMC. The IDMC may recommend terminating the study for unfavorable results at an interim analysis.

Interim Futility Analysis for CR

An interim futility analysis of the CR rate is planned when the 95th randomized participant has completed the Cycle 7 Day 1 assessment or discontinued treatment, whichever comes first. The study may be terminated at CR interim futility analysis, if the 1-sided p-value from the stratified CMH test comparing the CR rates (tamibarotene plus azacitidine treatment group versus placebo plus azacitidine treatment group) is CCI. The non-binding futility bound is derived using a Hwang-Shih-DeCani (HSD) spending function with gamma = -4 (Hwang 1990). Refer to Section 7.4.3 for a description of the analysis of the CR rate.

Interim Futility Analysis for OS

If the CR rate is statistically significant at the time of the primary efficacy analysis of the CR rates between the 2 treatment groups, an interim OS futility analysis will be conducted at the final CR analysis, which is when approximately **CC** information fraction (**C** of the total **CC** events) has been observed, and the boundary for OS will be updated based on actual observed information fractions at the interim. The study may be terminated at OS interim futility analysis if the 1-sided p-value from the stratified logrank test comparing the distribution of OS (tamibarotene plus azacitidine treatment group

versus placebo plus azacitidine treatment group) is **CCI**. The non-binding futility bound is derived using Lan-DeMets spending function. Refer to Section 7.4.4 for a description of the analysis of OS.

Table 16	Planned Stopping Boundaries for CR Futility Analysis and FA
----------	---

Endpoint	Look	IF	Number of Participants	Boundary (1-sided p-value)	Minimum Critical Difference of CR Rate at the Boundary
CR rate	Futility	0.5	CCI	CCI	0.0045
	FA	1	CCI	CCI	0.1349

Abbreviations: CR = complete remission; FA = final analysis; IF = information fraction.

Table 17	Planned Stopping	Boundaries for	OS Futility An	alysis and FA

Endpoint	Look	IF	Number of Events	Boundaries (1-sided p-value)	Approx. Observed Hazard Ratios at the Boundary
OS	Futility	0.249	CCI	CCI	1.261
	FA	1	CCI	CCI	0.78

Abbreviations: FA = final analysis; IF = information fraction; OS = overall survival

7.4.7.2 *Multiplicity Adjustments*

The study will be claimed positive when the primary endpoint (CR rate) is statistically significant. To maintain the overall type I error among the primary endpoint and the key secondary endpoint, the CR rate will be tested at 1-sided alpha of CCI, and if it is significant, OS will be tested at 1-sided alpha of CCI.

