9.4.2 Primary Endpoint

Complete Remission

CR will be determined by the investigator per the modified IWG MDS criteria (Cheson 2006). Per the IWG MDS criteria responses must last at least 4 weeks. Instructions for the assessment of IWG response including the provision of a 2-week window for unscheduled hematology evaluations to meet the IWG criteria of CR are provided in Section 8.1.1.

The CR will be evaluated in the Intent-to-Treat (ITT) population. CR rate and 95% exact binomial confidence intervals (CIs) will be calculated by treatment group. Patients who do not have any post-baseline response assessment will be considered as non-responders and will be included in the denominator. The stratified Cochran–Mantel–Haenszel (CMH) test will be applied to compare the CR rates between the 2 treatment groups, stratified by IPSS-R risk group (Intermediate, High, and Very High Risk) and by geographical region (North America, Western Europe, and Israel versus Eastern Europe). The final analysis of CR is planned for the time when all 190 patients have completed the Cycle 7 Day 1 response assessment or discontinued treatment, whichever comes first. Patients with missing response assessment data will be considered as a failure to achieve CR, including patients who have died, withdrew consent, or started a new treatment prior to achieving a CR.

The point estimate of the difference of the proportions for CR rate between the 2 treatment groups will also be provided along with 95% CI.

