6 INVESTIGATIONAL PLAN

6.1 Overall Study Design

This is a Phase 3, multi-center, randomized, double-blind, placebo-controlled study comparing the activity of tamibarotene plus azacitidine to placebo plus azacitidine as first-line therapy in retinoic acid receptor alpha (RARA)-positive participants with newly diagnosed higher-risk MDS (HR-MDS). Enrollment in countries in North America, Europe, and Israel is planned.

At the Pre-screening Visit, blood samples will be collected and sent to the Almac Diagnostics Laboratory for assessment of RARA biomarker to determine study eligibility. Pre-screening assessments for the RARA biomarker will be performed within 45 days of Cycle 1 Day 1, and screening assessments for all other eligibility criteria will be performed within 30 days of Cycle 1 Day 1.

Approximately CCI HR-MDS participants will be screened, with approximately participants randomized in the study. Participants will be randomized 2:1 to receive either tamibarotene plus azacitidine or placebo plus azacitidine. Randomization will be stratified by the Revised International Prognostic Scoring System (IPSS-R) risk group (Intermediate, High, and Very High Risk) and by geographical region (North America, Western Europe, plus Israel, and Eastern Europe).

Response will be assessed by the investigator per the modified International Working Group (IWG) MDS criteria (Cheson 2006). Bone marrow aspirates will be collected to measure response on Day 1 of Cycles 2 and 4, followed by every third cycle (7, 10, 13, etc.), with bone marrow aspirates collected at other times as clinically determined based upon clinical findings or changes in peripheral blood counts. Following the response assessment on Day 1 of Cycle 7, those in CR may have the frequency of bone marrow aspirates for response assessment reduced to every 6 cycles.

Participants will undergo response and safety evaluations throughout their study participation as detailed in the protocol Schedule of Activities (Section 1.3 in the study protocol). Participants may continue to receive study drug until experiencing an unacceptable toxicity, disease progression (including transformation into acute myeloid leukemia [AML]), relapse, decision to pursue post-remission therapy (such as HSCT) or an alternative anticancer therapy, participant withdraws consent, or the investigator determines it is in the best interest of the participant to discontinue study drug.

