7.4.3 Primary Efficacy Endpoint Analysis Methods

7.4.3.1 Primary Estimand Analysis for CR

The final analysis of CR is planned for the time when the first approximately **CCI** randomized participants out of the planned **CCI** participants have completed the Cycle 7 Day 1 response assessment or discontinued treatment, whichever comes first.

The primary endpoint is CR achieved by Cycle 7 Day 1, as determined by the investigator per the modified IWG MDS criteria (Cheson 2006). There is expected to be a high correlation between CR achieved by Cycle 7 Day 1 and CR achieved at any time (Silverman 2006; VIDAZA UPSI), and therefore, the same effect size and other design assumptions are justified in the hypothesis testing below. The objective is to demonstrate the superiority of tamibarotene plus azacitidine compared to placebo plus azacitidine in CR in RARA-positive newly diagnosed HR-MDS participants.

The null hypothesis (H₀) to be tested is:

In RARA-positive participants with newly diagnosed HR-MDS, CR rate for participants in the tamibarotene plus azacitidine treatment group is the same as the CR rate for participants in the placebo plus azacitidine treatment group.

The alternate hypothesis (H_A) to be tested is:

In RARA-positive participants with newly diagnosed HR-MDS, CR rate for participants in the tamibarotene plus azacitidine treatment group is higher than the CR rate for participants in the placebo plus azacitidine treatment group.

The following analyses will be conducted separately:

- [1] Primary analysis of primary estimand (investigator response in mITT analysis set)
- [2] Sensitivity analysis of primary estimand (investigator response in ITT analysis set)
- [3] Sensitivity analysis of primary estimand (investigator response in PP analysis set)

The CR rate and 95% exact binomial CIs based on the Clopper-Pearson exact method will be calculated by treatment group.

Confidential

Syros Pharmaceuticals, Inc. SY-1425-301

The CR rate will be analyzed using the Cochran-Mantel-Haenszel (CMH) test to compare the 2 treatment groups with a 1-sided 2.5% level of significance. The strata for the test will be those used for stratified randomization, with potential pooling of strata if there is insufficient information in any stratum; the pooling strategy is specified in Section 7.4.2. The point estimate of the difference of the proportions for CR rate between the 2 treatment groups will be provided along with its 95% CI.

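### The CR futility look is timed by one person, the 95th randomized participant, so an early treatment stop by that person brings the look forward to below its planned information fraction of 0.5.

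*SAP*

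**What the plan says.** SAP section 7.4.7.1 states that the futility look at CR "is planned when the 95th randomized participant has completed the Cycle 7 Day 1 assessment or discontinued treatment, whichever comes first". The test is the stratified CMH test. The bound is non-binding and comes from a Hwang-Shih-DeCani function with gamma = -4. Table 16 gives the planned looks as "CR rate Futility 0.5 CCI CCI 0.0045" and "FA 1 CCI CCI 0.1349", where CCI marks redacted cells.

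The final CR analysis is worded for a group. Protocol section 9.4.2 has it "planned for the time when all 190 patients have completed the Cycle 7 Day 1 response assessment". SAP section 7.4.3.1 ties it to the first N randomized (N redacted), when those "participants have completed the Cycle 7 Day 1 response assessment or discontinued treatment, whichever comes first".

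For OS, section 7.4.7.1 says the boundary will be updated to the information fraction actually observed. It says nothing similar for CR, and it names no analysis set for the interim CR test. The corresponding protocol text (synopsis and section 9.5) has lost the words where the trigger count stood, so it neither confirms nor corrects the SAP wording.

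**The concern.** The futility bound is set for half the information, but the trigger does not secure half the information. It depends on the treatment status of one person. Protocol section 7.1 lists many ordinary reasons for coming off study drug, such as toxicity, progression, withdrawal of consent to drug and investigator decision. If one of these applies to the 95th participant in the first weeks, the look is due at once, while many of the participants randomized shortly before are still months from Cycle 7 Day 1.

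At stake is a look that can lead the IDMC to recommend ending a Phase 3 trial. It would be made on fewer known outcomes, against a p-value bound that the chosen spending function would not give at that information level. The final CR analysis has a safeguard: SAP section 8.2.1 explains that the mITT set was added to secure at least six months of follow-up. The interim has none.

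**Working it through.** **1. The plan's own figures.** Information fraction: 95/190 = 0.50, as in Table 16. The final test is "with a 1-sided 2.5% level of significance", so the final standard error implied by Table 16 is 0.1349/1.96 = 0.0688. At half the information it is 0.0688 × √2 = 0.0973. The interim bound is then z = 0.0045/0.0973 = 0.046, a one-sided p of about 0.48. Design power is redacted. Solving the gamma = -4 boundary gives an interim critical difference of 0.0009, 0.0028, 0.0042 and 0.0047 at 80%, 85%, 90% and 95% power. The stated 0.0045 fits 90–95%; 90% is assumed below.

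**2. Outcomes pending at an early trigger.** Cycle 7 Day 1 falls 6 × 28 = 168 days, or 168/30.4375 = 5.52 months, after Cycle 1 Day 1. If the 95th participant stops at month *s* and accrual is *a* per month, about *a* × (5.52 − *s*) of the earlier participants are pending. Fitting 190 patients and their Cycle 7 Day 1 into the 70-month timeline needs at least 190/(70 − 5.5) = 2.9 per month on average. For *s* = 1, with no pending outcome known early:

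| Accrual per month (assumed) | Pending | Information fraction |
|---|---|---|
| 3 | 13.6 | (95 − 13.6)/190 = 0.43 |
| 5 | 22.6 | 0.38 |
| 8 | 36.2 | 0.31 |
| 12 | 54.2 | 0.21 |

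**3. Simulation.** Arrivals are Poisson at 4–10 per month; time to stopping is exponential, with 25–50% stopping before Cycle 7 Day 1. A participant is mature on reaching Cycle 7 Day 1 or stopping.
- When the 95th stops before Cycle 7 Day 1, on average about 70–87 of the first 95 are mature (10th percentile 49–79). That is 70/190 = 0.37 to 87/190 = 0.46.
- The overall chance that fewer than 85 are mature is about 11–37%.
- A first-month stop by the 95th has about 5–12% probability.

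A wider simulation (3–12 per month, 20–50% stopping) also credits CRs reached early and known outcomes in participants randomized after the 95th. The look then falls below 0.5 in about 16%, 25–27% and 34–35% of runs when 20%, 35% and 50% stop. A stop after month 3 gives a mean fraction of about 0.50–0.55, so the problem lies mainly in the first three months.

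**4. Effect on the decision.** At 90% power the function spends 0.10 × (e² − 1)/(e⁴ − 1) = 0.012 at fraction 0.5. With the 90%-power bound, z = 0.0042/0.0973 = 0.043, the drift θ satisfies θ√0.5 = 2.26 + 0.043, so θ = 3.26. Keeping that bound at fraction *t*, the chance of wrongly stopping is Φ(0.043 − θ√*t*):

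| *t* | False stop, bound kept | Spend intended at *t* | p bound intended at *t* |
|---|---|---|---|
| 0.50 | 1.2% | 1.2% | 0.48 |
| 0.45 | 1.6% | 0.9% | 0.57 |
| 0.40 | 2.2% | 0.7% | 0.65 |
| 0.30 | 4.1% | 0.4% | 0.80 |

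A simulation of the whole rule assumed CR rates of 35% and 13%. At 2:1 the pooled rate is (2 × 35 + 13)/3 = 27.7%, giving a final standard error of √(0.277 × 0.723/(190 × 2/9)) = 0.069, in line with step 1. False stopping was about 0.6–0.9% when all of the first 95 are mature, about 0.7–1.4% under the SAP trigger, and about 1–4% after a first-month stop. The base lies below 1.2% because the standard error under these rates is smaller than the pooled null value: for 95 patients, √(0.35 × 0.65/63.3 + 0.13 × 0.87/31.7) = 0.085 against 0.0973.

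**The case against.** The intended meaning can be guessed. With 95/190 = 0.5 and a final trigger worded for a group, the 95th participant may be shorthand for the last of the first 95. The look is non-binding and run by an independent committee that includes a statistician (Protocol section 10.1.4.1). It is only planned for that moment, and the IDMC Charter, which is not available here, may be more exact. The missing protocol text may also state the trigger properly. These points limit the severity. They do not remove the defect, because the only legible trigger names one person and will be followed as written.

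Three stronger readings are tempting, and the documents do not support them.
- A reader might infer that pending participants count as failures, and that diluted CR rates drive wrong stops. The SAP does not say who enters the interim test. Its list of non-responders (section 6.4.1.1) has no item for someone still on treatment and awaiting Cycle 7 Day 1, and CR can already be documented at Cycle 2 or 4 Day 1. With a bound near zero difference, counting pending participants as failures gave 0.65–0.96% false stops, against 0.67–1.01% when they were excluded.
- A reader might infer that any early stop by the 95th puts the look below half the information. After about month 3 the shortfall mostly disappears.
- A reader might take the event to be loss from the study. It is treatment discontinuation; someone who stops drug but stays in follow-up also triggers the look.

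**Conclusion.** Wrong as written, with low-to-moderate severity. Followed literally, the trigger can put the CR futility look below the information fraction in Table 16, with no provision to adjust the CR bound. The maturity figures rest on assumed accrual and discontinuation. The direction does not: with a first-month stop, the fraction was below 0.5 in essentially every run, even at 3 patients per month, close to the slowest average accrual that the timeline allows. The cost in decision error, at about 90% assumed power, is a few tenths of a percentage point of added false-stop risk overall and roughly 0.5–3 points after a month-1 stop. Nothing here threatens type I error or the final CR analysis.

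**What to change.** In SAP section 7.4.7.1, replace the single-participant trigger with: *when every one of the first 95 randomized participants has either had the Cycle 7 Day 1 response assessment or stopped study treatment*. State that the interim CMH test is based on those 95, and that the CR futility bound is recomputed at the actual information fraction, as is already planned for OS. Carry the same wording into the IDMC Charter, and check it against the unredacted protocol section 9.5.

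The cost is a short text change. The look then comes about 2.5–3 months later in the affected cases, or about 0.6–1.4 months later on average under the assumptions above. At least 95 outcomes are then known, so the fraction is at least 95/190 = 0.50 whoever stops early.

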7.4.7.3 Examination of Subgroups

The subgroup analyses will be conducted using the mITT analysis set for CR-related analyses.

To determine whether the treatment effect is consistent across various subgroups, subgroup analyses of the CR rate, based on whether participants achieved CR by Cycle 7 Day 1, will be performed for the participant subgroup categories listed below. For the geographical region subgroup, the 3 regions (North America, Western Europe, or Israel) were pooled together as 1 category in the subgroup analysis because these 3 regions and Eastern Europe may have differences in available supportive care treatments, access to subspecialty consultants, and highly specialized hospital care.

- IPSS-R Risk Status:
 - Intermediate
 - High
 - Very High
- Geographical Region:
 - North America, Western Europe, or Israel (3 pooled regions)
 - Eastern Europe
- Age Group:
 - ≥ 18 to <65
 - ≥ 65 to < 75
 - ≥75
- Gender:
 - Female
 - Male
- Race:
 - Asian
 - Black or African American
 - White
 - Other/Multiple
- Bone Marrow Blasts at Baseline:
 - ≤10%
 - >10% to <15%
 - ≥15%
- RARA Overexpression
 - 1st quartile
 - 2nd quartile
 - 3^{rd} quartile
 - 4th quartile
- ECOG
 - 0 or 1
 - 2 or 3
- Disease Type
 - Primary or not-treatment related MDS
 - Secondary or treatment related MDS
- TP53
 - Mutated

- Wild type
- Cytogenetic Risk Status
 - Very Good or Good
 - Intermediate
 - Poor
 - Very Poor
- ASXL1/TET2
 - ASXL1 mutated
 - ASXL1 wild type/TET2 mutated
 - ASXL1 wild type/TET2 wild type
- RUNX1
 - Mutated
 - Wild type
- DNMT3A
 - Mutated
 - Wild type
- TP53 Multihit
 - Yes
 - No
- Number of Mutated Genes
 - 0
 - 1
 - 2
 - ≥3

In addition, a subgroup analysis for genetic risk, potentially utilizing IPSS-Molecular (IPSS-M) risk category, may be performed. Detailed analysis will be performed separately, and this analysis is outside the scope of this SAP. Subgroup analyses of the different mutations will be based on central NGS data, if available, otherwise local laboratory results will be used.

A forest plot of the estimated treatment effect along with 95% CIs of CR rate will be provided by the subgroup factors listed above. A subgroup analysis may not be performed if the number of participants in the subgroup in each treatment group is not sufficiently large (e.g., <10%). Additional subgroup analyses may be performed post-hoc, as appropriate.

Subgroup analysis of OS will be performed based on the ITT Analysis Set for IPSS-R risk status, geographical region, age, race, gender and any other factors that are deemed appropriate.

7.5 Pharmacokinetic Evaluation

Concentration-time data for tamibarotene will be included in the CSR as listings. Other PK analysis will be provided in a separate report and is outside the scope of this SAP.

7.6 Safety Evaluation

All safety analyses will be conducted for Safety Analysis Set 1, unless otherwise specified. For safety analysis presented by study visit, the baseline value will be defined as the last non-missing value reported prior to the first study drug administration.

7.6.1 Adverse Events

Treatment-emergent adverse events (TEAEs) are defined as those AEs with onset after the first dose of study drug or existing events that worsened after the first dose during the study up until the last dose of study drug + 30 days. TEAEs will be summarized by treatment group. Selected TEAEs will also be summarized. The selected TEAEs include rash, pain, hypertriglyceridemia, venous thrombosis, anemia/RBC count decreased, thrombocytopenia/platelet count decreased, neutropenia/neutrophil count decreased, and leukopenia/white blood cell (WBC) count decreased. A detailed search strategy for the selected TEAE groups is provided in Appendix 1.

AEs with missing start and/or stop dates will be considered TEAEs. Imputation rules for partial and missing dates are described in Table 10.

Verbatim terms on CRFs will be mapped to PTs and SOCs using MedDRA, version 23.1 or higher. AEs will be graded using the National Cancer Institute (NCI) CTCAE version 5. If an AE grade is missing, the previous worst grade under the same PT will be assigned if it is available, otherwise a grade of 4 will be assigned for classification purposes in the TLFs.

The CTCAE Grade will be summarized by grouping Grade 1 and Grade 2 together, then Grade 3 and Grade 4 together, as well as Any Grade for all relevant TEAE tables.

Summaries of the following types will be presented by treatment group:

• Overall summary of the number of TEAEs, TEAEs by relationship to tamibarotene/placebo and azacitidine, TEAEs by CTCAE grade, serious AEs (SAEs), SAEs related to tamibarotene/placebo and azacitidine, selected TEAEs, TEAEs requiring concomitant medications, TEAEs leading to dose interruption of tamibarotene/placebo and azacitidine, TEAEs leading to dose reduction of tamibarotene/placebo and azacitidine, TEAEs leading to discontinuation of
tamibarotene/placebo and azacitidine, TEAEs leading to death (overall summary will also be analyzed based on mITT who received at least 1 study dose)

- TEAEs by SOC and PT
- TEAEs by PT
- TEAEs occurring in $\geq 10\%$ of participants in any treatment group by PT
- TEAEs related to tamibarotene/placebo by PT
- TEAEs related to azacitidine by PT
- TEAEs by CTCAE grade, SOC and PT
- TEAEs by CTCAE grade and PT
- TEAEs related to tamibarotene/placebo by CTCAE grade and PT
- TEAEs related to azacitidine by CTCAE grade and PT
- SAEs by SOC and PT
- SAEs by PT
- SAEs occurring in \geq 5% of participants in any treatment group by PT
- SAEs related to tamibarotene/placebo by PT
- SAEs related to azacitidine by PT
- Selected TEAEs by PT
- Selected TEAEs related to tamibarotene/placebo by PT
- Selected TEAEs related to azacitidine by PT
- Selected TEAEs by PT and CTCAE grade
- Selected TEAEs related to tamibarotene/placebo by PT and CTCAE grade
- Selected TEAEs related to azacitidine by PT and CTCAE grade
- TEAEs requiring concomitant medications by PT
- TEAEs related to tamibarotene/placebo requiring concomitant medications by PT
- TEAEs related to azacitidine requiring concomitant medications by PT
- TEAEs leading to dose interruption of tamibarotene/placebo by PT
- TEAEs leading to dose interruption of azacitidine by PT
- TEAEs leading to dose reduction of tamibarotene/placebo by PT
- TEAEs leading to dose reduction of azacitidine by PT
- TEAEs leading to discontinuation of tamibarotene/placebo by PT
- TEAEs leading to discontinuation of azacitidine by PT

The overall summary of TEAEs will also be created for Safety Analysis Set 2, while all other safety outputs will be created only for Safety Analysis Set 1.

All deaths will be summarized based on the number and percentage of participants. This summary will classify participants by time of death relative to the last dose of treatment (>30 days or \leq 30 days) and analyze the primary cause of death. Off-treatment deaths (deaths occurring >30 days after the last dose of treatment) will only be summarized at the prespecified IA and the final OS analysis or based on a regulatory request.

Summaries by SOC and PT will be ordered by descending incidence of SOC and PT within each SOC based on the tamibarotene plus azacitidine group. Summaries by PT will be ordered by descending incidence of PT for the tamibarotene plus azacitidine group. At each level of summarization (e.g., any AE, SOC, and PT), participants experiencing more than 1 TEAE will be counted only once. In the summary of TEAEs by severity grade, participants will be counted once at the highest severity reported at each level of summarization; in the summary of TEAEs by relationship, participants will be counted once at the closest relationship to the indicated study drug (tamibarotene/placebo or azacitidine).

AE data will be presented in data listings. SAEs, selected AEs, AEs requiring concomitant medications, AEs leading to dose interruption/dose reductions/discontinuation of study drug (tamibarotene or azacitidine), AEs leading to death, and deaths will be presented in separate data listings.

